8.4.4 Concomitant Medications

Concomitant medications will be assessed and includes any medication that would be taken during the study including all over the counter medications, vitamins, and nutritional supplements.

Medications used in this study will be coded by using latest version of World Health Organization (WHO) drug dictionaries.

Concomitant medications will be summarized descriptively using frequency tables by anatomical therapeutic chemical (ATC) class level 2 and preferred name by treatment group and overall based on ITT population. Concomitant medications will be listed. Additionally, a listing of subjects taking prohibited medications for intercurrent infections other than CT or GC will be provided.

8.5 Extent of Exposure

8.5.1 Treatment Adherence

Adherence with treatment gel usage during study (rate of product use adherence) will be estimated using the eDiary data.

Adherence ratio will be calculated as = [# of times product is properly used as noted in the eDiary / # of coital events noted during the treatment phase in the eDiary].

Study product adherence (compliance) will be calculated as: 100x [adherence ratio as calculated above]. The maximum percentage of doses used will be 100%.

Study drug compliance, number of times of product use (determined via eDiary), and number of times sexual intercourse occurred will be summarized descriptively by treatment group and overall using mITT population.

Study drug compliance will be summarized in categories “0%”, “>0% and <20%”, “≥20% and <40%”, “≥40% and <60%”, “≥60% and <80%”, “≥80% and <100%”, “≥80% and ≤100%”, and “100%” using frequency count and percentages. For the purposes of the frequency table, each compliance group will be deemed mutually exclusive (e.g., compliance rate of 41% would be in the ≥40% category only and would not be counted in the ≥20% category).

Study product distribution details and subject diary data will be listed.

8.6 Efficacy Analyses

This section addresses separately the analyses to be conducted on the primary, secondary, and exploratory efficacy endpoints.

8.6.1 Analysis Methods - Multiplicity

FDA Submission:

To control for multiple testing issues, a hierarchical testing strategy will be employed for exploratory endpoints that evaluate the efficacy of EVO100 vaginal gel in the prevention of urogenital CT and GC infection by assessing the proportions of subjects with:

- Overall sexual satisfaction using the FSFI overall sexual satisfaction question at Visit 5 and not having a CT or GC infection (Endpoint A), and
- Overall sexual satisfaction using the FSFI overall sexual satisfaction question at Visit 5 (Endpoint B).

If the primary endpoint is successful, then Endpoint A will be tested using a two-sided alpha=0.05. Endpoint B will be tested in succession if Endpoint A has a successful outcome.

EMA Submission:

For the EMA analysis, the primary endpoint can be either of the parallel primary endpoints for CT only and GC only. If either parallel primary endpoint is successful, then Endpoint A (same as above) will be tested using a two-sided alpha=0.05. Endpoint B (same as above) will be tested in succession if Endpoint A has a successful outcome.

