4 STUDY ENDPOINTS

4.1 Primary Endpoint

- The primary efficacy endpoint is the proportion of subjects who are defined as study successes versus study failures among the intervention groups (EVO100 or placebo).
Estimand Framework
 - FDA Submission
 - Success is defined as subjects completing the trial to Visit 5 without any of the following: CT/GC infection, usage of prohibited antibiotics during the study, an invalid CT/GC test at Visit 5.
 - The mITT population will be used, and the Chi-Square test will be used to compare the failure rates in EVO100 and placebo.
 - EMA Submission
 - The parallel primary efficacy endpoints define success through Visit 5 as:
 - CT Infection Endpoint:
 - The proportion of subjects without a CT infection, CT prohibited antibiotics, or invalid Visit 5 CT test.
 - GC Infection Endpoint
 - The proportion of subjects without a GC infection, GC prohibited antibiotics, or invalid Visit 5 GC test.
 - The mITT population will be used and the Chi-Square test will be used to compare the failure rates in EVO100 and placebo.

Note: These two parallel primary endpoints enable efficacy to be assessed separately for CT and GC. In this way, if the study is successful for either CT or GC but not for both, an indication for prevention of just one of the two pathogens could still be granted. Both primary endpoints will be tested at the 0.05 significance level (with no adjustments for multiplicity of statistical testing).

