4.3 Exploratory Endpoints

Exploratory assessments include:

- Comparison of the proportion of subjects with overall sexual satisfaction using the female sexual function index (FSFI) overall sexual satisfaction question at Visit 5 and not having a CT or GC infection.
- Comparison of the proportion of subjects with overall sexual satisfaction using the FSFI overall sexual satisfaction question at Visit 5.
- Comparison of the proportion of subjects reporting overall product satisfaction at Visit 5.

- Comparison of compliance with EVO100 vaginal gel usage versus placebo usage during study (rate of product use adherence versus placebo).
- Subgroup analyses of the primary endpoint (the proportion of subjects who are defined success versus failure) will be performed for the following:
 - Subjects with 0%, >0% and <20%, ≥20% and <40%, ≥40% and <60%, ≥60% and <80%, ≥80% and <100%, ≥80% and ≤100%, and 100% product use adherence.
- Descriptive analysis of failure components for the FDA and EMA primary endpoints.
- Comparison of PROMIS Sexual Function and Satisfaction (PROMIS SexFS), Pain and Lubrication subscales with EVO100 vaginal gel usage versus placebo.
- Comparison of FSFI Lubrication and Pain subscales with EVO100 vaginal gel usage versus placebo.
- Comparison of Patient Global Impression of Change (PGIC) with EVO100 vaginal gel usage versus placebo.

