5 SAMPLE SIZE AND POWER

The primary analysis is a comparison between proportion of subjects who are defined study successes versus study failures (success defined as subjects completing the trial to Visit 5 without any CT or GC infection and no use of prohibited antibiotics; failures defined as subjects with CT infection, GC infection, use of prohibited antibiotics, or loss to follow-up) among the intervention groups (EVO100 or placebo).

It is assumed that the proportion of subjects who will have CT infection, GC infection, use of prohibited antibiotics, or loss to follow-up will be 30.5% for active treatment versus 37.5% for placebo group based on the Phase 2B/3 study (EVO003) with equal lost to follow-ups assumed in both intervention groups. Using a Chi-Square test for the primary endpoint, 821 analyzable subjects per treatment group (1642 subjects total) will yield approximately 85% power to detect a rate difference of 7% with a 2-sided 5% type I error rate. Given the assumption that 5% of subjects are found to be positive at enrollment, the total sample size planned for this study is 1730 subjects. With an assumed screen failure rate of approximately 27.8%, 2397 subjects are estimated to be needed for screening.

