9 CHANGES TO PLANNED ANALYSIS FROM STUDY PROTOCOL

The following changes to the analysis plan have changed since the approval of the protocol:

- 1) Male condom usage summary statistics.
- 2) Assessing the effect of male condom usage on study success rates.
- 3) Added sensitivity analysis for the primary endpoint to check the impact of the use of prohibited medication.
- 4) Patients with duplicate enrollments will have their second entries will be excluded from all analyses
- 5) Added secondary analyses for separate CT and GC Only analyses. These analyses will serve as parallel primary endpoints for the EMA marketing authorization application.
- 6) An exploratory analysis of the FDA primary endpoint by subgroups of prior infection documentation status (available, not available)
- 7) A subgroup analysis of the FDA primary endpoint by Age groups (18-24, 25-45, 46-64, 65+)

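### On the EMA route, does opening Endpoints A and B at a full 0.05 after either CT or GC succeeds break a promised 5% error rate?

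*SAP*

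**What the plan says.** SAP Section 4.1 sets up CT and GC as parallel primary endpoints for the EMA: "Both primary endpoints will be tested at the 0.05 significance level (with no adjustments for multiplicity of statistical testing". The reason given is that, if only one endpoint succeeds, "an indication for prevention of just one of the two pathogens could still be granted". Section 9, item 5, confirms this use.

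Section 8.6.1 has two paragraphs. The FDA paragraph opens "To control for multiple testing issues, a hierarchical testing strategy will be employed for exploratory endpoints" and runs a fixed chain: the single composite primary, then Endpoint A (satisfied on the FSFI overall question at Visit 5 and free of CT and GC), then Endpoint B (the satisfaction question alone). The EMA paragraph reuses A and B with a different entry condition: "For the EMA analysis, the primary endpoint can be either of the parallel primary endpoints for CT only and GC only", and then "If either parallel primary endpoint is successful, then Endpoint A (same as above) will be tested using a two-sided alpha=0.05".

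Both A and B are listed in Section 4.3 as exploratory. Section 8.6.3 says the infection part of A follows the FDA primary endpoint rules.

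**The concern.** The FDA chain is valid across its three tests: one primary at 0.05 opens A, and A opens B. The EMA paragraph borrows the chain but replaces the single primary with an either-or condition over two tests, each already at 0.05. If CT succeeds, its 0.05 passes in full to A and then B, while GC is still tested at its own 0.05. Two branches then each carry 5%.

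The section's title is Multiplicity, so a reader could take a positive A or B on the EMA route as part of a 5% familywise procedure. If so, the chance of a false GC or B claim could approach 10% where 5% was expected. The case in question, success on one pathogen only, is one that Section 4.1 expressly plans for.

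**Working it through.** **1. The plan's own figure.** Section 5 gives failure rates of 37.5% and 30.5%, 821 analyzable subjects per arm, two-sided 0.05 and about 85% power. The pooled rate is 0.34, so the null standard error is √(2 × 0.34 × 0.66 / 821) = 0.02338; the unpooled one is 0.02332. Power = Φ[(0.07 − 1.96 × 0.02338) / 0.02332] = Φ(1.04) = 85.0%. This reproduces. It applies to the composite, with loss to follow-up counted as failure. The SAP gives no power for CT or GC alone, and no familywise figure for the EMA route.

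**2. Where the entry rule can add error.**

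- *Neither pathogen responds.* A opens only after a false CT or GC result, so a false A or B always accompanies an error already counted. Total: 1 − 0.95² = 9.75% if independent, and at most 10%. This comes wholly from Section 4.1.
- *Both respond.* No false pathogen claim is possible, and error within A and B is at most 5%. If A is null, it is one 0.05 test and B needs A first. If only B is null, B is one 0.05 test.
- *One responds (say CT) and the other does not.* Here the rule adds error.

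**3. Size in the third case.** Take CT and A effective, GC and B null, tests independent:

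P(false GC or B) = 0.05 + 0.95 × power(CT) × power(A) × 0.05

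The first 0.05 is the disclosed GC test; the second term is what the entry rule adds. All powers below are assumed.

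| Power CT | Power A | Total | Added |
|---|---|---|---|
| 100% | 100% | 9.75% | 4.75 points |
| 85% | 85% | 8.4% | 3.4 points |
| 70% | 70% | 7.3% | 2.3 points |
| 50% | 30% | 5.7% | 0.7 points |

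With assumed correlations (CT-GC 0.3; A with CT, GC and B 0.5; B with CT or GC 0), simulated totals are 9.7%, 8.0%, 7.2% and 6.2%.

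**4. A power for A that fits the SAP.** A is FDA success and satisfaction together. If satisfaction does not differ between arms (B null) and is independent of infection, A's rates are the Section 5 success rates (62.5% placebo, 69.5% EVO100) times the satisfaction rate, which the documents do not give. With 821 per arm, the step 1 formula and CT power assumed at 85%:

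| Assumed satisfaction | A: placebo vs EVO100 | Power A | Added = 0.95 × 0.85 × power(A) × 0.05 |
|---|---|---|---|
| 90% | 56.25% vs 62.55% | 74% | 3.0 points |
| 80% | 50.0% vs 55.6% | 62% | 2.5 points |
| 70% | 43.75% vs 48.65% | 51% | 2.1 points |

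With CT power at 100%, the additions are 3.5, 3.0 and 2.4 points. The 4.75-point case needs A power near 100%, which these rates do not support; it is a theoretical bound.

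**5. What the alternatives would do.**

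- *Label A and B nominal on the EMA route.* No test, threshold or probability of a false result changes.
- *Open A only if both CT and GC succeed.* Joint error is 5% when one pathogen responds. With CT at 85% power and GC null, A would open 0.85 × 0.05 = 4% of the time, against 1 − 0.15 × 0.95 = 86% now. When neither responds, the figure stays at 9.75%.
- *Test CT and GC at 0.025 each.* A test with 85% power at 0.05 falls to 77%. Under Holm it falls to 78% if the other pathogen is null, and to 83% if the other also has 85% power.

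**The case for a change.** The strongest reply is that a section on multiplicity should not give endpoints a formal conditional test at a stated alpha and leave the status of the result unclear. Either the condition is meant to control error jointly, which on the EMA route it does not, or the p-values are nominal and the SAP should say so. The disclosure in Section 4.1 covers CT and GC only and is silent on A and B. The size can also exceed 2 to 3 points: if A is null as well and CT has 85% power, the total is 1 − 0.95 × (1 − 0.85 × 0.05) = 9.0%, an addition of 4.0 points.

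The mechanism and arithmetic stand. The inference does not. The sentence about controlling multiple testing sits under the FDA heading and concerns exploratory endpoints. Error within that pair stays at or below 5% on both routes, so its stated purpose is met. The 9.0% case needs A to be null although CT responds. A counts infection-free status, so under the independence assumption in step 4 a CT effect that carries into the FDA composite moves A too. As for unclear status, Sections 2.3, 4.3, 8.6.1 and 8.6.3 all treat these endpoints as exploratory, and the SAP attaches no EMA claim to them.

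**Conclusion.** The observation is correct but calls for no change. On the EMA route A and B have no joint 5% control with CT and GC, and the SAP does not say that they do. Each pathogen claim keeps its own 5%, error within A and B is at most 5%, and the 9.75% maximum for independent tests follows from the disclosed and reasoned choice to test the pathogens separately. When only one pathogen responds and B is null, the entry rule adds about 2 to 3 points. That size rests on 85% CT power, Section 5 success rates, 70% to 90% satisfaction independent of infection, and independent tests.

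No alternative improves the plan enough to justify adopting it. A nominal label restates the exploratory status. Requiring both pathogens would nearly close A and B in the one-pathogen case that the design is meant to allow. Splitting alpha or using Holm would take power from the primary endpoints to protect exploratory ones. An analyst reporting the EMA results would read the A and B p-values as exploratory in any event.

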8.6.2 Analysis of Primary Endpoints

FDA Submission

For the primary analysis, the proportion of subjects who are defined study successes (i.e., have

all of the following through Visit 5: no CT/GC infection, no use of prohibited antibiotics, not lost to follow-up/otherwise discontinued, and no invalid CT/GC test at Visit 5) will be compared between the intervention groups (EVO100 or placebo) using a Chi-Square test. The primary efficacy analysis will be completed using the subjects deemed analyzable* from the mITT population.

*All subjects in the mITT population are deemed analyzable for the purpose of the primary endpoint analysis. Those subjects who are in ITT but not in mITT will be excluded from said analysis. The primary analysis will be performed using all subjects in the mITT population.

The primary statistical hypothesis being tested is that there is no difference in the proportion of subjects deemed study success in the EVO100 intervention group versus placebo. In statistical terms:

$$H_0: p_{EVO100} = p_{placebo}, H_A: p_{EVO100} \neq p_{placebo}$$

where, p_{EVO100} and $p_{placebo}$ denote the proportion of subjects deemed a study success while on EVO100 or placebo, respectively. Denominators for percentages are number of subjects in the mITT population in each intervention group. To test superiority over placebo, the percentage of study successes will be compared against placebo based using Chi-Square test. The estimated difference in proportions, 95% confidence interval, and p-value will be presented. A two-sided 5% type I error rate ($\alpha=0.05$) will be used. The Fisher's Exact test will be conducted in place of the Chi-Square test if necessary due to issues with the expected cell counts.

For the primary endpoint and exploratory analyses using CT/GC infection, any subject that does not have a known infection status through Visit 5 (i.e., at least through study day 105) (e.g., is deemed lost to follow-up) will be considered a failure. Likewise, any subject that uses prohibited antibiotics during the treatment period of the study regardless of CT/GC infection status will be considered a primary endpoint failure. Lastly, a patient having an invalid CT/GC test at Visit 5 will be considered a failure.

Secondary analyses of CT only and GC only endpoints will be performed as specified in the below EMA analysis section. See that section for more details.

In addition, a sensitivity analysis will be provided for the primary endpoint. For the sensitivity analysis, the proportion of subjects who are defined as study successes will be irrespective of the use of prohibited antibiotics. Success will be defined as no CT/GC infection through Visit 5 (i.e., at least through study day 105). The statistical analysis described for the primary endpoint will be used for the secondary and sensitivity analyses.

A listing will be provided for CT/GC NAAT sample result.

EMA Analysis

For the parallel primary analyses, the proportion of subjects who are defined study successes will be compared between intervention groups (EVO100 or placebo) using a Chi-Square test. The primary efficacy will be completed using the subjects deemed analyzable* from the mITT population.

*All subjects in the mITT population are deemed analyzable for the purpose of the primary endpoint analysis. Those subjects who are in ITT but not in mITT will be excluded from said

analysis. The primary analysis will be performed using all subjects in the mITT population.

For the CT infection endpoint, success will be defined as having no CT infection, taking no CT prohibited medications, and no invalid CT test at Visit 5. For the GC infection endpoint, successes will be defined as having no GC infection, taking no GC prohibited medications, and no invalid GC test at Visit 5.

The primary statistical hypothesis being tested is that there is no difference in the proportion of subjects deemed study success in the EVO100 intervention group versus placebo. In statistical terms:

$$H0: pEVO100 = pplacebo, HA: pEVO100 \neq pplacebo$$

where, pEVO100 and pplacebo denote the proportion of subjects deemed a study success while on EVO100 or placebo, respectively. Denominators for percentages are number of subjects in the mITT population in each intervention group. To test superiority over placebo, the percentage of study successes will be compared against placebo based using Chi-Square test. The estimated difference in proportions, 95% confidence interval, and p-value will be presented. A two-sided 5% type I error rate ($\alpha=0.05$) will be used. The Fisher's Exact test will be conducted in place of the Chi-Square test if necessary due to issues with the expected cell counts.

For the primary endpoint, any subject that does not have a known infection status through Visit 5 (i.e., at least through study day 105) (e.g., is deemed lost to follow-up/otherwise discontinued) will be considered as having a negative CT/GC test through Visit 5.

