3 STUDY DESIGN

3.1 General Study Design

At total of 1730 women, ages ≥ 18 , who had a documented urogenital CT or GC infection or an undocumented self-reported CT or GC infection with risk factors, at any time over the 17 weeks preceding the enrollment visit, or positive at screening visit will be enrolled. A high prevalence of CT infection has been observed in those who were treated for urogenital chlamydial infection during the preceding several months. The second infection may result from infection through an untreated partner or exposure through a new partner. By including only women who have had a CT or GC infection within the past 17 weeks, this study targets those at high risk for infection.

At screening, subjects will be tested for a current GC/CT infection by nucleic acid amplification test (NAAT) via vaginal swab. Those negative for current infection will be enrolled. Those who test positive for CT/GC infection at screening will receive standard of care treatment. To meet eligibility criteria, these subjects will not be enrolled until 3 to 4 weeks after screening (at least 21 days after treatment).

[figure not shown]
Eligible participants will be enrolled and randomized 1:1 (865 subjects per treatment arm) to either EVO100 Gel, 5g or HEC placebo 5 g supplied in a pre-filled, single-dose applicator. A baseline vaginal pH and a full gynecologic examination (including bimanual and speculum) will be obtained at enrollment.

Subjects are instructed to apply EVO100 or placebo gel immediately before or up to one hour prior to coitus for the duration of the 16-week intervention period. EVO100 or placebo is to be re-applied in the same manner for each occurrence of sexual intercourse. Subjects will keep an electronic diary (eDiary) to document sexual activity and product use.

Every 4 weeks (5 visits), all subjects will return to the clinic for repeat CT/GC NAAT (vaginal swab), urine pregnancy (urinary β -human chorionic gonadotrophin [uHCG]) testing, eDiary review, and return of unused investigational product. At Visits 2 to 4, subjects will be re-supplied with EVO100 or placebo gel. At Visit 5, subjects will return unused investigational product and continue to use their eDiaries but will not be resupplied with EVO100 or placebo gel.

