8.4.2 Baseline and Disease Characteristics

The baseline characteristics includes CT/GC infection history, gynecological exam details, current contraceptive methods used, vaginal pH, CT/GC NAAT sample result, risk factors and vital signs. Categorical variables summarized using frequency counts and continuous variables will be summarised by descriptive statistics using ITT population. Baseline characteristics will be listed.

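### The FDA and EMA primary analyses use an unadjusted Chi-Square test; pre-specified adjustment for the randomisation stratum and baseline risk factors would add some precision without enrolling more women

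*SAP*

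**What the plan says.** - **FDA primary.** In SAP 8.6.2 the composite success proportions "will be compared between the intervention groups (EVO100 or placebo) using a Chi-Square test", with Fisher's exact test as fallback. The difference in proportions, its 95% confidence interval and a p-value are reported.
- **EMA parallel primaries.** In the same section, success on the CT endpoint and on the GC endpoint "will be compared between intervention groups (EVO100 or placebo) using a Chi-Square test".
- **Supporting analyses.** "The statistical analysis described for the primary endpoint will be used for the secondary and sensitivity analyses". No adjusted result is therefore planned even as a back-up.
- **Randomisation.** SAP 3.2 stratifies by whether documentation of the prior infection is available.
- **Baseline data.** SAP 8.4.2 summarises infection history and contraceptive methods together with "vaginal pH, CT/GC NAAT sample result, risk factors and vital signs".
- **Eligibility.** Inclusion criterion 1 in the protocol synopsis asks for at least one listed risk factor when the prior infection is documented and at least two when it is not. The list covers young age, a new partner, more than one partner, a partner with other partners or a known STI, and inconsistent condom use.
- **Where baseline factors meet efficacy.** Documentation status (SAP 8.6.3 and section 9) and age group (section 9) define subgroup displays of the FDA endpoint. No stratified or covariate-adjusted test appears anywhere, and no reason is given.

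**The concern.** The plan selects women on factors that it regards as markers of infection risk, records risk factors at baseline, stratifies randomisation on a variable tied to how many of them a woman must have, and then analyses the result as if none of this were known.

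In a randomised comparison, adjusting for prognostic baseline values and standardising back to the whole analysis population estimates the same difference in proportions. It removes the part of the outcome variance that those values explain, and it corrects chance imbalance in them. Leaving the stratum out also means that the Chi-Square takes no credit for the balance that stratification creates, which tends to make it slightly conservative if the stratum is prognostic.

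What is at stake is precision in the primary confidence intervals and a modest amount of power. Validity is not at stake.

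**Working it through.** **1. Reproduce the plan's figure.** Inputs from SAP section 5: failure "30.5% for active treatment versus 37.5% for placebo group", 821 analyzable women per arm, "approximately 85% power to detect a rate difference of 7% with a 2-sided 5% type I error rate". For a Chi-Square with pooled variance and no continuity correction:

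power = Φ{ [Δ√n − 1.96 √(2p̄(1−p̄))] / √(p₁(1−p₁) + p₂(1−p₂)) }

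- Δ = 0.375 − 0.305 = 0.07, and Δ√821 = 2.006.
- p̄ = 0.34, √(2 × 0.34 × 0.66) = 0.670, and 1.96 × 0.670 = 1.313.
- √(0.375 × 0.625 + 0.305 × 0.695) = 0.668.
- (2.006 − 1.313) / 0.668 = 1.037, and Φ(1.037) = 0.850.

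The sample size matches the crude test.

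**2. Effect of adjustment on the FDA composite.** Let R² be the share of outcome variance explained by the baseline covariates. Adjustment then acts like an effective n per arm of 821/(1 − R²). The documents give no R², so the range is assumed.

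| Assumed R² | Effective n per arm | Extra women, both arms | Power |
|---|---|---|---|
| 0 | 821.0 | 0 | 85.0% |
| 0.5% | 825.1 | 8 | 85.2% |
| 1% | 829.3 | 17 | 85.4% |
| 2% | 837.8 | 34 | 85.7% |
| 5% | 864.2 | 86 | 86.8% |
| 10% | 912.2 | 182 | 88.5% |

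**3. Simulation check.** 821 per arm, 1:1 allocation stratified on one factor, and four independent binary covariates with assumed prevalences of 30%, 50%, 50% and 40%. The crude Chi-Square was compared with a logistic model standardised to the whole sample with an influence-function standard error, using 4000 runs per scenario.

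| Assumed odds ratios | R² | Power, crude to adjusted | Null rejection, crude / adjusted |
|---|---|---|---|
| 1.2 each | 0.7% | 85.2% to 85.4% | 5.2% / 5.3% |
| 1.5 each | 3.4% | 86.1% to 87.5% | 4.8% / 5.2% |
| 2, 2, 1.5, 1.5 | 6.3% | 86.0% to 87.8% | 4.5% / 5.0% |
| 2.5, 2.5, 2, 2 | 11.7% | 86.5% to 89.5% | 4.9% / 5.6% |

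The gains are 0.2, 1.4, 1.8 and 3.0 points, in line with step 2. The Monte Carlo standard error of a null rate is √(0.05 × 0.95/4000) = 0.34 points. The adjusted test rejects slightly more often than the crude test in each null scenario, and its largest value, 5.6%, is within two standard errors of 5%.

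**4. EMA endpoints.** The documents give no CT-only or GC-only failure rates. As an illustration, assume placebo failure of 5% to 25% and the composite's relative effect (0.305/0.375 = 0.813). Crude power at 821 per arm is then 15% to 62%, and R² = 5% would add about 0.5 to 2 points. These are not predictions: both the rates and the R² are assumed.

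**The case against.** The strongest reply is that the Chi-Square is valid, pre-specified and matched to its sample size, so adjustment is a preference. The first part stands. A reader might infer that the test is wrong or that the trial is undersized because of it; the reproduction in step 1 rules that out.

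Three other inferences go further than the documents allow.

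- **That baseline risk is ignored altogether.** It is not. Age and documentation status each define a planned subgroup display. The accurate statement is that nothing is adjusted for.
- **That the stratum says nothing about risk.** The rule of one versus two risk factors ties documentation status to risk by design, so the stratum belongs in the adjustment.
- **That SAP 3.1 shows the proposed covariates to be prognostic in this trial.** It says "A high prevalence of CT infection has been observed in those who were treated for urogenital chlamydial infection during the preceding several months". That explains why the whole sample is at high risk. It does not show that any factor separates risk among the women enrolled.

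The objection to the size of the gain also stands in large part. Requiring risk factors for entry narrows their spread, and the FDA composite counts loss to follow-up, prohibited antibiotics and invalid tests as failures, which infection risk factors need not predict. An illustration assumes six independent factors with at least one required, four of them prognostic (odds ratios 2, 2, 1.5, 1.5), and average failure of 34%. R² is 5.7% if every failure is an infection. It falls to 3.6% or 1.6% if 10 or 20 points of failure are unrelated to risk, with power of 87.0%, 86.3% and 85.6%. The dilution would be smaller if those failures also track the covariates. For EMA, counting unknown status as negative weakens the association too.

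Finally, SAP 8.4.2 lists risk factors without showing that each was recorded for every woman, so a rule for missing covariates is needed.

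**Conclusion.** The point holds as an efficiency improvement. All primary analyses are unadjusted, while the stratum and the risk factors are part of the trial's own design and baseline data. On the FDA composite, power at 821 per arm would move from 85.0% to about 85.2% to 88.5% for an assumed R² of 0.5% to 10%, and the lower part of that range is the more plausible.

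A reader might also infer that adjustment would restore the 90% power planned in the protocol synopsis. The documents do not support that: the two figures rest on different failure rates, and the assumed range stops short of 90%.

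The EMA gain cannot be computed from stated rates. It is likely smaller, since each single-pathogen endpoint probably has fewer events. If the covariates turn out weak, almost nothing is lost at this sample size, which is why the change is still worth making.

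**What to change.** Before unblinding, amend SAP 8.6.2 as follows.

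1. Make each primary analysis (FDA composite, CT, GC) a covariate-adjusted risk difference from a logistic working model, standardised to the mITT population, with a robust standard error. The hypothesis, population and failure rules stay as written.
2. Fix the covariates in advance: the randomisation stratum; age under 25 versus 25 or over; screening NAAT positive and treated versus negative; more than one partner or a partner with other partners; new partner in the past 12 weeks.
3. State a simple rule for missing covariate values that drops no woman from the mITT, such as a missing-indicator category.
4. State a reduced covariate list, with the stratum kept, for any endpoint with few events.
5. Keep the Chi-Square, with Fisher's exact test as fallback, as a supportive result.

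The cost is SAP wording and a few lines of code. It needs no additional women and, provided the listed factors were recorded individually, no new data. That should be confirmed before the covariate list is fixed.
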